**Hypothesis #2:** Reduced total stress perfusion deficit, a semi-quantitative score that combines scar and ischemia.

**AIM 2.** To test the hypothesis that LDM at a target dose of 15 to 20 mg orally weekly for 1-12 months will, compared to placebo, result in improved left ventricular (LV) myocardial mechanics, as assessed by transthoracic echocardiography, and that this functional improvement will be correlated with the change in coronary flow reserve after 1-12 months of treatment. In this population of patients without severe heart failure, we propose to test the following hypotheses:

**Hypothesis #3:** LDM for 1-12 months will result in improved LV systolic function, as assessed by measures of LV peak global longitudinal strain, and diastolic function, as assessed by measures of tissue Doppler mitral annular early diastolic relaxation velocity (E').

**Hypothesis #4:** Changes in LV systolic and diastolic function after 1-12 months of LDM therapy will be correlated with changes in coronary flow reserve.

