**Exclusion criteria:**

- a. Prior history of chronic infectious disease, tuberculosis, or severe fungal disease; chronic hepatitis B or C infection; renal insufficiency; interstitial pneumonitis, bronchiectasis, or pulmonary fibrosis; known chronic pericardial effusion, pleural effusion, or ascites; chronic liver disease; myeloproliferative disorders in the past 5 years; non-basal cell malignancy or treated lymphoproliferative disease within the past 5 years; known HIV positive; life expectancy of <3 years;
- b. Chronic inflammatory condition such as lupus or rheumatoid arthritis, ulcerative colitis or Crohn's disease
- c. White blood cell count <3,500/ul, hematocrit < 32 percent, or platelet count < 75,000/ul
- d. Liver transaminase levels (AST or ALT) >upper limit of normal (ULN) or albumin < the lower limit of normal (LLN);
- e. Creatinine clearance < 40 ml/min as estimated with the Cockcroft-Gault equation;
- f. History of alcohol abuse or unwillingness to limit alcohol consumption to less than 4 drinks per week
- g. Women of child bearing potential, even if they are currently using contraception, and women intending to breastfeed.
- h. Men who plan to father children during the study period or who are unwilling to use effective forms of contraception.
- i. Requirement for use of drugs that alter folate metabolism (trimethoprim/sulfamethoxazol) or reduce tubular excretion (probenecid) or known allergies to antibiotics making avoidance of trimethoprim impossible;
- j. Current indication for methotrexate therapy;
- k. Chronic use of oral steroid therapy or other immunosuppressive or biologic response modifiers (see Exclusionary Medication List in Manual of Operations). Eligible study participants will be encouraged to have up to date pneumococcal and influenza vaccinations as recommended based on their age and underlying medical conditions.
- l. Chest X-ray evidence in the past 12 months of interstitial pneumonitis, bronchiectasis, or pulmonary fibrosis. For participants who do not have a chest X-ray in the prior 12 months, a chest X-ray will be obtained at baseline as part of the study protocol.
- m. New York Heart Association Class IV congestive heart failure.

[figure not shown]

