**Methods:** 2-D echocardiograms will be performed at the 3 enrolling imaging sites at baseline and 12 months after randomization in accordance with standard clinical practice and utilizing a standardized study protocol as outlined in section V. As described in section V, we have previously demonstrated feasibility of measuring cardiac mechanics with high reproducibility. The primary efficacy endpoints for *Aim 2* are the change in LV peak global longitudinal strain (GLS) (systolic function) and in tissue Doppler mitral annular early diastolic relaxation velocity (E') (diastolic function). Key secondary endpoints are change in other LV systolic function measures (LVEF and tissue Doppler peak systolic mitral annular velocity (S')), as well as change in other LV diastolic function measures (LV early diastolic strain rate by speckle-tracking, and mitral inflow Doppler E velocity to E' ratio (E/E')). Tertiary endpoints include changes in more conventional measures of LV structure (e.g. volumes, wall thickness, mass) over 1-12 months.

**Statistical analyses. Hypothesis 3:** We will use separate linear regression models with the respective change in LV peak GLS and E' over 1-12 months as the outcome variables. Each of these regression models will control for baseline variables of stratum (DM or metabolic syndrome), time since index MI (< 6 months or ≥ 6 months), imaging site (BWH, OHI, or UAB), the corresponding baseline LV peak GLS and E' scores, as well as treatment assignment.

**Hypothesis 4:** Although temporality cannot be established in correlational analysis of concurrent changes, we will also use regression models to clarify the association of changes in CFR and LV function. Controlling for treatment assignment, baseline stratification variables, baseline CFR and LV function, as well as change in LV function, our outcome will be change in CFR. By adding the baseline and change in LV function to our primary model for *Aim 2*, we will explore whether changes in CFR are associated with changes in LV function, or whether independent treatment effects remain.

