**Power calculations:** For *Aim 2*, we used prior publications from our team to characterize the reproducibility of the LV measures of systolic and diastolic function. Power analysis is based upon the following assumptions: the expected effect size is 10% relative improvement in each of the primary and secondary outcome measures in the active treatment group compared to placebo. **Table 2** shows the sample size needed to reach 80-90% power for each of the primary and secondary efficacy measures. As for *Aim 1*, estimated power by this approach should be considered conservative since the control for baseline scores is expected to enhance power. Of the 150 patients we expect to randomize, there will be at least 130 evaluable subjects completing the study (estimating a 10-15% attrition rate between time of randomization and final echo).

**Table 2.** Power and sample size calculations for Aim 2

AIM 2 Measurement	Difference (LDM vs. placebo)	Standard deviation (placebo)	Two-sided $\alpha$ level	Total sample size for power		
				80%	85%	90%
Primary outcome:						
Systolic: $\Delta\text{GLS}_{\text{peak}}$	1.4%	2.8	0.05	126	142	166
Diastolic: $\Delta\text{E}'_{\text{velocity}}$	0.7 cm/s	1.3	0.05	112	126	148
Secondary outcomes:						
Systolic: $\Delta\text{S}'$	0.6 cm/s	1.2	0.05	128	146	172
$\Delta\text{LVEF}$	1.5%	3.1	0.05	138	156	182
Diastolic: $\Delta\text{E}/\text{E}'$	1.1	2.0	0.05	128	146	172
$\Delta\text{LAVI}$	1.2 ml/m 	2.3	0.05	118	134	158

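### Table 2: the E/E' sample sizes do not follow from that row's difference and SD and equal the S' row's, and the LVEF difference does not fit the stated 10% relative improvement

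*Combined protocol and SAP*

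**What the plan says.** Section VI, Aim 2, Power calculations, sets one effect-size rule for all the echocardiographic outcomes: "the expected effect size is 10% relative improvement in each of the primary and secondary outcome measures in the active treatment group". It then says that Table 2 "shows the sample size needed to reach 80-90% power for each of the primary and secondary efficacy measures". No baseline or placebo mean is given for any of these measures.

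Three rows of Table 2 matter here. The entries are difference, SD, two-sided alpha, and total N for 80%, 85% and 90% power.

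- E/E': "1.1 2.0 0.05 128 146 172"
- S': "0.6 cm/s 1.2 0.05 128 146 172"
- LVEF: "1.5% 3.1 0.05 138 156 182"

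The Aim 2 Methods paragraph names all three among its key secondary endpoints, in the sentence that begins "Key secondary endpoints are change in other LV systolic function measures". On the population, Section II (Aim 2) says "In this population of patients without severe heart failure", and exclusion criterion m in Section III is "New York Heart Association Class IV congestive heart failure".

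**The concern.** The E/E' and S' rows print the same three totals, but their standardized differences are not the same: 1.1/2.0 = 0.55 against 0.6/1.2 = 0.50. With the same alpha, allocation and power, two different ratios cannot need the same sample sizes at all three power levels. At least one E/E' entry is therefore wrong. If it is the totals, the table understates the power for that endpoint. If it is the difference or the SD, the planning assumption itself is misreported.

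The LVEF row raises a different question. Its totals may be correct for its inputs, but a 1.5-point difference is hard to square with a rule of 10% relative improvement in every measure. A reader who takes the rule at face value would think the trial was planned around a much larger LVEF change than the table uses, and could misread a null LVEF result.

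**Working it through.** **Inputs.** Differences, SDs and two-sided alpha 0.05 come from Tables 1 and 2. Allocation is 1:1 (Section V). The totals count evaluable patients: the Aim 1 power text gives 130 evaluable as 85% power for CFR, which is the 85% column of Table 1.

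**Method.** Two-sample t-test, two-sided 0.05, total N = 2 × (n per arm, rounded up). The normal approximation is total N = 4(z₀.₉₇₅ + z_power)² / (difference/SD)²; the t version adds about 2.

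**Step 1: reproduce the plan's own figures.**

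| Row | Difference / SD | Ratio | Computed (80/85/90%) | Printed |
|---|---|---|---|---|
| CFR | 0.24 / 0.45 | 0.533 | 114/130/150 | 114/130/150 |
| TPD stress | 2.5 / 4.9 | 0.510 | 124/140/164 | 124/140/164 |
| GLS | 1.4 / 2.8 | 0.500 | 128/146/172 | 126/142/166 |
| E' | 0.7 / 1.3 | 0.538 | 112/126/148 | 112/126/148 |
| S' | 0.6 / 1.2 | 0.500 | 128/146/172 | 128/146/172 |
| LVEF | 1.5 / 3.1 | 0.484 | 138/156/182 | 138/156/182 |
| LAVI | 1.2 / 2.3 | 0.522 | 118/134/158 | 118/134/158 |
| **E/E'** | **1.1 / 2.0** | **0.550** | **106/122/142** | **128/146/172** |

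Six of the eight rows match exactly. The small GLS gap is consistent with rounding: 1.42/2.8, which prints as 1.4/2.8, gives 126/142/166. E/E' is the only row that cannot be reproduced.

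**Step 2: E/E' by hand, normal approximation at 80% power.** 4 × (1.960 + 0.842)² / 0.55² = 31.4 / 0.3025 = 103.8, so 104 (106 with the t-test). The printed total is 128. The ratios of printed to computed are 128/106 = 1.21, 146/122 = 1.20 and 172/142 = 1.21.

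**Step 3: can something else explain the row?**

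- *Rounding.* A difference of 1.05–1.15 and an SD of 1.95–2.05 allow ratios from 1.05/2.05 = 0.512 to 1.15/1.95 = 0.590. The least favourable, 0.512, gives 122/140/164, still below the printed totals.
- *One-sided alpha.* This gives 82/96/114 (normal approximation), further away.
- *Dropout inflation.* 106/0.85, 122/0.85 and 142/0.85 give 125/144/168. This is close but matches none of the three, and no other row is inflated.
- *A mistyped input.* 1.0/2.0 and 1.1/2.2 both have ratio 0.50, and both give exactly 128/146/172.

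**Step 4: power for E/E'.** At the printed inputs (ratio 0.55), N = 128, 146 and 172 give 87.0%, 91.0% and 94.8%, not 80%, 85% and 90%. At 130 evaluable, power is 87.5% if the ratio is 0.55 and 80.8% if it is 0.50.

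**Step 5: LVEF against the 10% rule.** The mean at which 1.5 points is a 10% change is 1.5/0.10 = 15%. Rounding of the difference (1.45–1.55) gives 14.5–15.5%. The documents give no mean LVEF, so I assume a range of 40–65%:

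- 1.5/40 = 3.8% relative and 1.5/65 = 2.3% relative.
- A 10% relative change would be 4.0 to 6.5 points, which is 4.0/1.5 = 2.7 to 6.5/1.5 = 4.3 times the listed difference.

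**The case against.** The strongest reply concerns consequence. The plan commits to no particular power for Aim 2: the 85% figure applies only to CFR, and Table 2 offers a range of 80–90%. At 130 evaluable patients, E/E' exceeds 80% whichever entry is wrong. Needing more than 130 for 85% power is also not peculiar to E/E'; the printed GLS, S', LVEF and LAVI rows need 142, 146, 156 and 134. If the totals are the error, it runs in the safe direction. All of this stands, and it is why the point is minor. It does not make the row correct.

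On LVEF, the reply is that no baseline mean is stated, that NYHA class grades symptoms rather than ejection fraction, and that the eligibility criteria set no LVEF limit. The row's totals also follow exactly from 1.5 and 3.1, so only an introductory sentence is in question. This stands in part. The documents do not strictly rule out a mean LVEF of 15%, so the supportable statement is that the 10% claim is implausible for LVEF rather than impossible. The inconsistency remains, because the text applies the rule to each measure without exception and describes the patients as free of severe heart failure.

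**Conclusion.** The concern holds, at minor severity.

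The E/E' part rests on the documents alone. The printed totals are about 20% higher than the row's difference and SD require, and they are the totals for a ratio of 0.50, the same as the S' row. Copied totals and a mistyped difference or SD would each explain this, and the documents do not show which occurred.

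The LVEF part is firm on the arithmetic (10% implies a mean of 15%). That the claim fails rests on the description of the population and on an assumed mean, though the conclusion is the same across 40–65%. The LVEF totals themselves are correct for the listed inputs; what fails is the statement that the difference is a 10% relative improvement.

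The primary CFR calculation and the target of 150 randomized and 130 evaluable do not depend on Table 2.

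**What to change.** Check the E/E' row against the source calculation. If 1.1 and 2.0 are right, replace the totals with 106/122/142. If the totals are right, correct the mistyped difference or SD so that the ratio is 0.50.

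For LVEF, state the reference mean and the relative change that 1.5 points represents. Alternatively, drop the claim of 10% in each measure and let the absolute differences in Table 2 stand as the planning assumptions.

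The cost is one table row and one sentence, with no change to enrolment, endpoints or analysis.

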## V. STUDY PROCEDURES

Randomization and double-blind study treatment period to either placebo or LDM (1:1) of willing and eligible patients will occur at the end of the open label run-in phase per the parent CIRT protocol, and will be stratified by time since the qualifying event ( $< 6$  or  $\geq 6$  months from the date of MI or most recent angiogram), type of event (MI or multivessel CAD), presence of either type 2 DM or metabolic syndrome, and site, which will ensure balance in the proposed study. Patients willing to participate in CIRT will be asked to enroll into the sub-study and may sign the CIRT-CFR informed consent at any point between signing the parent CIRT informed consent and completing the parent CIRT randomization visit (Visit 4). After giving informed consent for the ancillary CIRT-CFR, patients will undergo the baseline PET scan along with echocardiography at any point between the parent CIRT post run-in visit (Visit 3) and up to 4 weeks after randomization (Visit 4). Per the parent CIRT protocol: i) blood will be collected and stored for biomarkers at baseline (Visit 3), ii) patients will complete quality of life (SF-36) questionnaires at enrollment (Visit 2) and 1-12 months (Visit 7) after randomization, and iii) patients will be called at 3, 6, and 10 months after randomization to assure compliance. Final PET scan and echocardiogram will occur at approximately 1-12 months after randomization or within 4 weeks ( $\pm 2$  weeks) of Visit 7. At that time, blood will be collected and stored for biomarkers (using the same protocol as in the parent CIRT) to coincide with follow-up imaging in CIRT-CFR. The data collection schedule for CIRT and CIRT-CFR is summarized in the Appendix. Trial schema is as follows:

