Imaging will be performed at the 3 imaging centers (BWH, OHI, and UAB). To minimize participant and site burden, only a baseline and single follow-up imaging time point will be pursued. The CIRT-CFR Screening Visit has been incorporated into the Consent Visit in an attempt to further reduce participant and site burden. Imaging tests (PET and echo) will be scheduled on the same day for patient convenience if possible, and no more than one week apart. “Baseline” study visit imaging will follow the open label run-in period of the parent trial to enhance long-term compliance and eliminate risk of radiation exposure for any individuals with immediate intolerance to the LDM study protocol. The imaging tests proposed are non-invasive, routinely performed, and historically well tolerated by patients. The radiation incurred through PET scanning is small ( $\sim 2.8$  mSv per study), and comparable to that incurred by an average American in a given year from background radiation. Clinical coordinators will be encouraged to enroll all CIRT-eligible patients at the 5 clinical sites participating in this ancillary study, so as to remove the possibility of selection bias. To minimize and understand potential selection bias, we will maintain an evaluation log of all patients who were screened and enrolled at the 6 sites.

**Timing of baseline imaging assessments.** Baseline PET scanning and echocardiography will follow CIRT's post run-in (open label, 6-8 week run-in phase) visit. The justification for this decision is based on the pharmacodynamics of LDM in rheumatoid arthritis, as well as additional biologic and trial logistic reasons. There are no data on the timing of changes in myocardial blood flow following LDM. Methotrexate is a prodrug that becomes active only when polyglutamated within cells, a slow iterative process that can take as long as ~27 weeks to reach steady state. In patients with rheumatoid arthritis, a clinical response to methotrexate usually begins within the first 6–12 weeks after initiation of therapy, with a maximal response observed at 6 months. This suggests that the longer-chain polyglutamates, which take longer to become detectable and reach steady state, have a more important role in the clinical response to methotrexate.

**Timing of follow-up imaging assessments.** Follow-up PET scanning and echocardiography will occur between 1 and 12 months post randomization.

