**Exploratory analyses:** The proposed ancillary study will not be powered to detect changes in clinical outcomes, patient symptoms, or changes in circulating biomarkers. However, we recognize the importance of exploring the correlations between the changes in CFR and LV function over the 1-12-month observation period and these meaningful outcomes. We propose the following exploratory tertiary objectives: (1) Explore an interaction between the change in CFR at 1-12 months with composite MACE that includes cardiac and all-cause mortality, recurrent MI, stroke, coronary revascularization, and hospitalization for unstable angina requiring unplanned revascularization or for congestive heart failure, occurring 3-4 years after randomization. We will use a proportional hazards model to explore relationships of CFR and its change with time until development of the first clinical event occurring through the end of randomization. We recognize that this exploratory analysis, in particular, will be limited because we expect only ~25 composite events in total in our study sample. (2) Correlate the change in CFR at 1-12 months with the corresponding change in QOL scores, as assessed by the standardized SF-36 Health Survey to be administered during enrollment, 12-month, and final study visits of the parent CIRT trial. Prior assessments with this tool have shown significant differences in baseline and 6-month follow-up scores in a modest-sized (n=120) patient population post-MI. (3) Correlate the change in CFR and LV function with the corresponding changes in circulating biomarkers of inflammation (hsCRP, IL-1) and myocardial strain (NTproBNP, hsTroponin), as assessed from stored biorepository samples at 8, 12 and 24 months after randomization. Analyses of changes in QOL scores and biomarkers will use linear regression models, after transforming changes to normality as necessary, and with control for baseline trial stratification variables, baseline QOL scores and biomarker levels, and treatment assignment. Main independent variables will be baseline and 1-12-month change in CFR. (4) Assess correlations among the baseline PET, echo, biomarker, and SF-36 data using linear regression models, as described above for continuous variables.

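### Exploratory objectives (1) and (3): name the blood drawn at the follow-up scan as the biomarker follow-up value, and start the CFR-change event model at that scan (low priority)

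*Combined protocol and SAP*

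**What the plan says.** Section VI, Exploratory analyses, objective (3) relates the changes in CFR and LV function to the corresponding changes in inflammation and myocardial-strain biomarkers, "as assessed from stored biorepository samples at 8, 12 and 24 months after randomization". The model statement for objectives (2) and (3) adds: "Main independent variables will be baseline and 1-12-month change in CFR".

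Section V places biomarker blood at Visit 3 for baseline. For follow-up, at the time of the final scan, "blood will be collected and stored for biomarkers (using the same protocol as in the parent CIRT) to coincide with follow-up imaging in CIRT-CFR". On when that scan happens, Section V says "Final PET scan and echocardiogram will occur at approximately 1-12 months after randomization or within 4 weeks" (plus or minus 2 weeks) of Visit 7, and then "Follow-up PET scanning and echocardiography will occur between 1 and 12 months post randomization". Section VI, Aim 2 Methods, is narrower for echo: "2-D echocardiograms will be performed at the 3 enrolling imaging sites at baseline and 12 months after randomization".

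Objective (1) relates CFR change to composite MACE "occurring 3-4 years after randomization", using a proportional hazards model for "time until development of the first clinical event occurring through the end of randomization". The plan expects about 25 composite events in total and says that this limits the analysis.

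**The concern.** In objective (3), change in CFR and change in biomarker are meant to correspond. If a scan is done early and the biomarker comes from month 8 or later, the two changes cover different intervals. Section V itself says that active methotrexate can take about 27 weeks to level off, and that the response in rheumatoid arthritis peaks at 6 months. A weak correlation could then reflect the time gap rather than biology, although a matched sample is already being stored.

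In objective (1), CFR change does not exist until the follow-up scan. With a clock that starts at randomization, as the reference to years after randomization implies, three things follow:

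- Patients who die before the scan have no value.
- Patients with a value have by definition survived to the scan.
- A nonfatal MI or revascularization between the two scans, each a component of the composite, may change the CFR that is then used to predict it. An association could run from event to CFR.

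**Working it through.** **1. Gap between scan and listed samples, objective (3).** Inputs: samples at months 8, 12 and 24 (Section VI); scans at 1-12 months (Section V). Gap = |sample month - scan month|.

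| Scan month | To month 8 | To month 12 | To month 24 | Nearest |
|---|---|---|---|---|
| 1 | 7 | 11 | 23 | 7 |
| 3 | 5 | 9 | 21 | 5 |
| 6 | 2 | 6 | 18 | 2 |
| 8 | 0 | 4 | 16 | 0 |
| 12 | 4 | 0 | 12 | 0 |

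The 24-month sample is 12 months or more after any scan done at 1-12 months. If scans were spread evenly over months 1-12 (an assumption), the mean gap to the nearest sample would be (7 x 3.5 + 2 x 1 + 2 x 1)/11 = 2.6 months. With the imaging-visit sample the follow-up gap is about zero whatever the timing.

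**2. Where scans probably fall.** Section V gives the SF-36 at Visits 2 and 7; Section VI gives it at the enrollment, 12-month and final visits. Matching the two makes Visit 7 the 12-month visit. Aim 2 Methods puts the follow-up echo at 12 months, and Section V keeps PET and echo within a week of each other. For scans done on that schedule, the 12-month sample already fits. Section V still permits scans from month 1.

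**3. The ~25 events.** This figure cannot be rebuilt, because no event rate is given for the broader composite. As a plausibility check only, the parent trial's 530 primary endpoints in 7,000 patients scale to 530/7,000 x 150 = 11.4. The broader composite would be higher by an unstated amount. I take 25 as given.

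**4. Events before the scan, objective (1).** Inputs: 25 events; follow-up F = 36 or 48 months (the plan's 3-4 years); N = 150 randomized or 130 evaluable; scan at month t.

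- Even timing: 25 x t/F, with mean t = 6.5 for evenly spread scans.
- Constant hazard: h = -ln(1 - 25/N)/F, events = N(1 - exp(-ht)), averaged over t = 1 to 12 for evenly spread scans. Example: N = 150, F = 36 gives h = 0.1823/36 = 0.00506 per month; at month 12, 150 x (1 - exp(-0.0608)) = 8.84.

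| Scans | Even, F=36 | Even, F=48 | N=150, F=36 | N=150, F=48 | N=130, F=36 | N=130, F=48 |
|---|---|---|---|---|---|---|
| Month 1 | 0.69 | 0.52 | 0.76 | 0.57 | 0.77 | 0.58 |
| Spread evenly | 4.51 | 3.39 | 4.84 | 3.65 | 4.90 | 3.69 |
| Month 12 | 8.33 | 6.25 | 8.84 | 6.68 | 8.93 | 6.76 |

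Events left after the scan are 25 minus these: about 24 (month 1), 20-22 (spread evenly), 16-19 (month 12).

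**5. Is there a rule elsewhere?** Section VI, Aim 1 Statistical analyses, drops patients without a repeat PET, but only from the primary and secondary analyses. It does not reach this tertiary model, nor patients who are scanned after a nonfatal event.

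**The case against.** The strongest reply on objective (3) is that Section V gives no other purpose for blood drawn with the scan, so the authors surely meant it to be available here. A reader might infer that the plan rejects that sample in favor of fixed months. The text does not support that: it omits the sample and does not exclude it. A reader might also infer that most scans are badly mismatched. The documents do not give the distribution of scan times, and what they do say points toward month 12. Both replies stand, and they reduce this part to an unresolved pairing that matters for early scans.

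On objective (1), a post-randomization covariate is not wrong in an association analysis, the time origin is only implied, and the plan admits that the model is limited. That also stands. What remains is the absence of a clock start at the scan and of a rule for earlier events. Reading the phrase about years 3-4 as late events only would remove pre-scan events, but it sits badly with a first-event analysis and with ~25 events in total. A reader might instead put all the events into the parent trial's two-year minimum and find a much larger pre-scan share. The exploratory objective speaks of 3-4 years and the parent trial averages 3, so that scenario is not supported.

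**Conclusion.** The point holds as a low-priority improvement to two unpowered exploratory objectives. In objective (3), early scans are not concurrent with any listed sample (7 months apart at month 1, 2 months at month 6). For scans near month 12 the gain from a change is small. In objective (1), about 0.5-1, 3-5 or 6-9 of ~25 events would precede month-1, evenly spread or month-12 scans.

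These counts are illustrations. They assume even timing or constant hazard over 3-4 years; early-weighted risk would raise them, and deaths before the scan would lower the number entering the model. The largest biomarker gaps need early scans and the largest pre-scan counts need late ones, so the two worst cases cannot occur together. The Appendix's data collection schedule was not in the text available for review, so the 8-, 12- and 24-month draws could not be matched to visits there.

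Nothing here supports a wider inference about the randomized Aim 1 or Aim 2 comparisons, which use neither model.

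**What to change.** **Objective (3).** Name the sample drawn at the follow-up imaging visit as the follow-up value, with Visit 3 as baseline, and make the 8-, 12- and 24-month samples secondary. Note that baseline PET may be done up to 4 weeks after randomization, so pairing it with Visit 3 blood is only approximate.

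**Objective (1).**
- Start the CFR-change model at the follow-up PET (a landmark; a time-dependent covariate is an acceptable alternative) and count only later events.
- State how patients with a nonfatal event between scans are handled.
- Start the baseline-CFR model at the baseline PET, or use delayed entry, since that scan can also follow randomization.
- Replace the end of randomization, evidently a slip, with the end of follow-up.

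**Cost.** SAP wording only; the blood draw and both scans are already planned. The CFR-change model keeps about 16-24 of the ~25 events, depending on scan timing. For the baseline-CFR model the loss should be below one event, since a 4-week delay is shorter than the month-1 case (0.5-0.8 events).
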